12.0 Informed Consent

Please see separate informed consent letter document (Appendix C)

13. Additional Elements

There are no known risks from being in this study, and participants will not benefit personally. However, we hope that others may benefit in the future from what we learn as a result of this study.

Participation comes at no additional cost to the participant. Participation is entirely voluntary and participants can withdraw from the study at any time simply by indicating that they do not wish to continue. Should participants withdraw from the study, they are not penalized for benefits for which they otherwise qualify. This study anticipates a maximum of 288 participants, with a maximum of 12 participants at each state tobacco control program site.

Appendices

Appendix A. Program Sustainability Assessment Tool (PSAT) Survey

Program Sustainability Assessment Tool

What is program sustainability capacity?

We define program sustainability capacity as *the ability to maintain programming and its benefits over time.*

Why is program sustainability capacity important?

Programs at all levels and settings struggle with their sustainability capacity. Unfortunately, when programs are forced to shut down, hard won improvements in public health, clinical care, or social service outcomes can dissolve. To maintain these benefits to society, stakeholders must understand all of the factors that contribute to program sustainability. With knowledge of these critical factors, stakeholders can build program *capacity* for sustainability and position their efforts for long term success.

What is the purpose of this tool?

This tool will enable you to assess your program's current capacity for sustainability across a range of specific organizational and contextual factors. Your responses will identify sustainability strengths and challenges. You can then use results to guide sustainability action planning for your program.

Helpful definitions

This tool has been designed for use with a wide variety of programs, both large and small, across different settings. Given this flexibility, it is important for you to think through how you are defining your program, organization, and community before starting the assessment.

Below are a few definitions of terms that are frequently used throughout the tool.

Program refers to the set of formal organized activities that you want to sustain over time. Such activities could occur at the local, state, national, or international level and in a variety of settings.

Organization encompasses all the parent organizations or agencies in which the program is housed. Depending on your program, the organization may refer to a national, state, or local department, a nonprofit organization, a hospital, etc.

Community refers to the stakeholders who may benefit from or who may guide the program. This could include local residents, organizational leaders, decision-makers, etc. Community does not refer to a specific town or neighborhood.

The name of the program or set of activities I am assessing is:

In the following questions, you will rate your program across a range of specific factors that affect sustainability. Please respond to as many items as possible. If you truly feel you are not able to answer an item, you may select "NA." **For each statement, circle the number that best indicates the extent to which your program has or does the following things.**

Environmental Support: Having a supportive internal and external climate for your program

1. Champions exist who strongly support the program.

Likert [1: To little or no extent; 2; 3; 4; 5; 6; 7: To a very great extent; or Not able to answer]

2. The program has strong champions with the ability to garner resources.

Likert [1: To little or no extent; 2; 3; 4; 5; 6; 7: To a very great extent; or Not able to answer]

3. The program has leadership support from within the larger organization.

Likert [1: To little or no extent; 2; 3; 4; 5; 6; 7: To a very great extent; or Not able to answer]

NA 4. The program has leadership support from outside of the organization. 1 2 3 4 5 6 7 NA

5. The program has strong public support.

Likert [1: To little or no extent; 2; 3; 4; 5; 6; 7: To a very great extent; or Not able to answer]

Funding Stability: Establishing a consistent financial base for your program

1. The program exists in a supportive state economic climate.

Likert [1: To little or no extent; 2; 3; 4; 5; 6; 7: To a very great extent; or Not able to answer]

2. The program implements policies to help ensure sustained funding.

Likert [1: To little or no extent; 2; 3; 4; 5; 6; 7: To a very great extent; or Not able to answer]

3. The program is funded through a variety of sources.

Likert [1: To little or no extent; 2; 3; 4; 5; 6; 7: To a very great extent; or Not able to answer]

4. The program has a combination of stable and flexible funding.

Likert [1: To little or no extent; 2; 3; 4; 5; 6; 7: To a very great extent; or Not able to answer]

5. The program has sustained funding.

Likert [1: To little or no extent; 2; 3; 4; 5; 6; 7: To a very great extent; or Not able to answer]

Partnerships: Cultivating connections between your program and its stakeholders

1. Diverse community organizations are invested in the success of the program.

Likert [1: To little or no extent; 2; 3; 4; 5; 6; 7: To a very great extent; or Not able to answer]

2. The program communicates with community leaders.

Likert [1: To little or no extent; 2; 3; 4; 5; 6; 7: To a very great extent; or Not able to answer]

3. Community leaders are involved with the program.

Likert [1: To little or no extent; 2; 3; 4; 5; 6; 7: To a very great extent; or Not able to answer]

4. Community members are passionately committed to the program.

Likert [1: To little or no extent; 2; 3; 4; 5; 6; 7: To a very great extent; or Not able to answer]

5. The community is engaged in the development of the program goals.

Likert [1: To little or no extent; 2; 3; 4; 5; 6; 7: To a very great extent; or Not able to answer]

Organizational Capacity: Having the internal support and resources needed to effectively manage your program and its activities

1. The program is well integrated into the operations of the organization.

Likert [1: To little or no extent; 2; 3; 4; 5; 6; 7: To a very great extent; or Not able to answer]

2. Organizational systems are in place to support the various program needs.

Likert [1: To little or no extent; 2; 3; 4; 5; 6; 7: To a very great extent; or Not able to answer]

3. Leadership effectively articulates the vision of the program to external partners.

Likert [1: To little or no extent; 2; 3; 4; 5; 6; 7: To a very great extent; or Not able to answer]

4. Leadership efficiently manages staff and other resources.

Likert [1: To little or no extent; 2; 3; 4; 5; 6; 7: To a very great extent; or Not able to answer]

5. The program has adequate staff to complete the program's goals.

Likert [1: To little or no extent; 2; 3; 4; 5; 6; 7: To a very great extent; or Not able to answer]

Program Evaluation: Assessing your program to inform planning and document results

1. The program has the capacity for quality program evaluation.

Likert [1: To little or no extent; 2; 3; 4; 5; 6; 7: To a very great extent; or Not able to answer]

2. The program reports short term and intermediate outcomes.

Likert [1: To little or no extent; 2; 3; 4; 5; 6; 7: To a very great extent; or Not able to answer]

3. Evaluation results inform program planning and implementation.

Likert [1: To little or no extent; 2; 3; 4; 5; 6; 7: To a very great extent; or Not able to answer]

4. Program evaluation results are used to demonstrate successes to funders and other key stakeholders.

Likert [1: To little or no extent; 2; 3; 4; 5; 6; 7: To a very great extent; or Not able to answer]

5. The program provides strong evidence to the public that the program works.

Likert [1: To little or no extent; 2; 3; 4; 5; 6; 7: To a very great extent; or Not able to answer]

Program Adaptation: Taking actions that adapt your program to ensure its ongoing effectiveness

1. The program periodically reviews the evidence base.

Likert [1: To little or no extent; 2; 3; 4; 5; 6; 7: To a very great extent; or Not able to answer]

2. The program adapts strategies as needed.

Likert [1: To little or no extent; 2; 3; 4; 5; 6; 7: To a very great extent; or Not able to answer]

3. The program adapts to new science.

Likert [1: To little or no extent; 2; 3; 4; 5; 6; 7: To a very great extent; or Not able to answer]

4. The program proactively adapts to changes in the environment.

Likert [1: To little or no extent; 2; 3; 4; 5; 6; 7: To a very great extent; or Not able to answer]

5. The program makes decision about which components are ineffective and should not continue.

Likert [1: To little or no extent; 2; 3; 4; 5; 6; 7: To a very great extent; or Not able to answer]

Communications: Strategic communication with stakeholders and the public about your program

1. The program has communication strategies to secure and maintain public support.

Likert [1: To little or no extent; 2; 3; 4; 5; 6; 7: To a very great extent; or Not able to answer]

2. Program staff communicate the need for the program to the public.

Likert [1: To little or no extent; 2; 3; 4; 5; 6; 7: To a very great extent; or Not able to answer]

3. The program is marketed in a way that generates interest.

Likert [1: To little or no extent; 2; 3; 4; 5; 6; 7: To a very great extent; or Not able to answer]

4. The program increases community awareness of the issue.

Likert [1: To little or no extent; 2; 3; 4; 5; 6; 7: To a very great extent; or Not able to answer]

5. The program demonstrates its value to the public.

Likert [1: To little or no extent; 2; 3; 4; 5; 6; 7: To a very great extent; or Not able to answer]

Strategic Planning: Using processes that guide your programs direction, goals, and strategies

1. The program plans for future resource needs.

Likert [1: To little or no extent; 2; 3; 4; 5; 6; 7: To a very great extent; or Not able to answer]

2. The program has a long-term financial plan.

Likert [1: To little or no extent; 2; 3; 4; 5; 6; 7: To a very great extent; or Not able to answer]

3. The program has a sustainability plan.

Likert [1: To little or no extent; 2; 3; 4; 5; 6; 7: To a very great extent; or Not able to answer]

4. The program's goals are understood by all stakeholders.

Likert [1: To little or no extent; 2; 3; 4; 5; 6; 7: To a very great extent; or Not able to answer]

5. The program clearly outlines roles and responsibilities for all stakeholders.

Likert [1: To little or no extent; 2; 3; 4; 5; 6; 7: To a very great extent; or Not able to answer]

Appendix B. Data Collection Form for Workshop

I. DOSAGE DELIVERED:

number of units of an intervention delivered or provided

1. # Stakeholders to complete PSAT
2. # Stakeholders to attend training
3. # Stakeholders to attend TA calls
4. # hours of training
5. # hours of TA

II. DOSAGE RECEIVED:

extent to which participants engage with or use materials or recommended resources.

Service-Related Questions related to Comprehension- required for properly completing tools

1. After viewing the Introduction to Sustainability Webinar, I now understand the concept of program sustainability completely (5 point Likert scale strongly agree- strongly disagree).
2. After attending/viewing the Action Planning Workshop, I now understand the process of Program Sustainability Action Planning completely (5 point Likert scale strongly agree- strongly disagree).
3. The handouts provided helped me to understand the Action Planning Workshop material (5 point Likert scale strongly agree- strongly disagree).

Action Plan Implementation-Related Questions (Implementation- “measures the extent to which users engaged with or used”)

1. My program created a program sustainability action plan based on the results of the Program Sustainability Assessment Tool and Action Planning Training (Y/N).
2. My program implemented the activities outlined in our program sustainability Action Plan (Y/N).
3. Please indicate the percentage of your sustainability plan your program has implemented (i.e., If you met 3 out 4 objectives, you would select 75%).

_____ 10% or less _____ 25% _____ 50% _____ 75% _____ 90% or more

4. Please estimate the amount of time per month your sustainability plan was discussed among staff.

_____ Less than 1 hour per month _____ 1-3 hours _____ 3-5 hours _____ 5-7 hours _____ 7-9 hours _____ 10+

5. Please estimate the amount of time per month your program staff focused on implementing your sustainability plan steps.

Less than 1 hour per month 1-3 hours 3-5 hours 5-7 hours 7-9 hours 10+

III. PARTICIPANT REACTION

Service Delivery: PSAT and Report-Related Questions (Relevance, Satisfaction)

1. I found the Program Sustainability Assessment Tool to be informative (5 point Likert scale strongly agree- strongly disagree).
2. The Program Sustainability Assessment Tool and Report helped me to think about program sustainability in ways I hadn't considered before (5 point Likert scale strongly agree- strongly disagree).
3. My program's future planning was impacted positively by the process of completing the Program Sustainability Assessment Tool (5 point Likert scale strongly agree- strongly disagree).
4. Planning for my program's sustainability was made easier by completing the Program Sustainability Assessment Tool (5 point Likert scale strongly agree- strongly disagree).

Service Delivery: Action Planning Training-Related Questions (Relevance, Satisfaction)

1. Objectives of the Action Planning Training were useful for my work (5 point Likert scale strongly agree- strongly disagree).
2. Objectives of the Action Planning Training were clearly articulated (5 point Likert scale strongly agree- strongly disagree).
3. Objectives of the training were achieved during the Action Planning Training (5 point Likert scale strongly agree- strongly disagree).
4. Overall, how would you rate the quality of the facilitator's presentation for the Action Planning Training? (5 point Likert scale excellent- poor).
5. The length of the Action Planning Training was: (3 point Likert scale too long- too short).
6. The Action Planning Training made planning for my program's sustainability easier. (5 point Likert scale strongly agree- strongly disagree).
7. The Action Planning Training was beneficial for my program. (5 point Likert scale strongly agree- strongly disagree).

8. The Action Planning Training was directly relevant to my program. (5 point Likert scale strongly agree- strongly disagree).
9. Overall, how satisfied were you with the Action Planning Training? (5 point Likert scale very satisfied to - very dissatisfied).

Service Delivery: Technical Assistance-Related Questions (Relevance, Satisfaction)

1. The technical assistance provided following the Action Planning Training was beneficial for my program. (5 point Likert scale strongly agree- strongly disagree).

2. The technical assistance provided following the Action Planning Training was directly relevant to my program. (5 point Likert scale strongly agree- strongly disagree).

3. The technical assistance provided following the Action Planning Training made planning for my program's sustainability easier. (5 point Likert scale strongly agree- strongly disagree).

4. Overall, how satisfied were you with the technical assistance provided following the Action Planning Training? (5 point Likert scale very satisfied to - very dissatisfied).

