Comparison state programs will participate in the PSAT assessment, record abstraction, and a key informant interview and survey with state program managers at three time points. Before taking the PSAT, we will work with the state tobacco control program manager to identify the list of TC stakeholders who will be involved in workgroup based on our standardized workgroup selection criteria.³¹ Once a list is determined, we will work with the program manager to plan a time to conduct an “Introduction to Sustainability” webinar. This webinar is identical to the webinar issued to the intervention group, because state programs will be informed of their group selection after completing the PSAT. The webinar educates listeners on the Program Sustainability Framework (8 domains), defines the parameters one should use when completing PSAT items (i.e., define the “program”), explains how to complete the PSAT online, and provides a time for state-specific Q & A. Prior to the webinar, we will ask the program manager and all stakeholders to complete an *optional* Qualtrics survey, assessing general state tobacco control program sustainability perceptions and individual demographics (age, gender, race, per NIH reporting requirements). Personally identifiable information will not be collected. The pre-workshop webinar is important for two reasons: (1) it familiarizes all workgroup members with the components of sustainability as outlined in our framework, and (2) introduces the PSAT and steps for completing the PSAT online. The webinar instructs users to answer N/A to PSAT items they are unable to accurately assess. The pre-workshop webinar generally lasts 45 minutes. Comparison states will receive a detailed sustainability assessment report outlining the state’s PSAT scores. There will also be follow-up correspondence, discussing state-level aggregated results of the PSAT, as well as recommendations for action planning next steps. At this point, we will provide a brief packet with resources about program sustainability. However, comparison states will not receive any other component of the training until year four of this project, when they will disseminate the finalized curriculum materials. Some comparison states might independently implement sustainability plans over the course of the grant. We will track implementation and account for it in analyses.

Phase 2 (Aim 2)

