To incorporate the influence of idiosyncratic characteristics of the state programs, longitudinal regression analysis will be used to model the outcome for each of the dependent variables. This analysis is modeled in Equation 1.

$$\beta_0 + \beta_1 PSAT_{i,t=0} + \beta_2 G_i + \beta_3 D_{it} + \beta_4 (G_{it} * D_{it}) + B_{5-k} X_{it} = Y_{it}$$

Equation 1

where i = state, t = time 1 or 2, $PSAT_{i,t=0}$ = baseline PSAT score, G_i = group (intervention or comparison), D_{it} = dose variable, $(G_{it} * D_{it})$ = an interaction between the group and dose terms, X_{it} = a vector of programmatic, organizational, community and funder variables, and Y_{it} = the

Figure 4. Sample size and power calculation

outcome variable. This analysis will ultimately be used to test Hypothesis 1, that the impact of the training is nonzero and positive.

$$H_0: \hat{\beta}_{intervention} = 0 \quad H_a: \hat{\beta}_{intervention} > 0$$

Hypothesis 1

The multivariate approach allows us to account for the numerous influences found in programmatic, organizational, community, and funder attributes. Data collection at different time points also allows for measuring changes in these variables, and the influence these changes have on institutionalization outcomes. In addition, the level of adoption and implementation of action plans both from the training (intervention states) and from other initiatives (comparison states) will vary across programs and time. Varying levels of action plan implementation across states must be acknowledged. Multivariate longitudinal analyses also allow us to control for differing degrees of dosage reception and delivery. We have successfully used similar dose variables.^{111,112}

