10.0 Recordkeeping

The Principal Investigator, [name], will be responsible for monitoring the data safety and quality of the overall study. This is a minimal risk study that does not warrant a formal Data Safety Monitoring Board.

Program Sustainability Assessment Tool (PSAT). The PSAT is a 40-item measure of a program's sustainability capacity which requires 10-15 minutes to complete. Individuals selected by state TC program managers will be invited to complete the PSAT online via our secure website <https://sustaintool.org/>. Data collected through the website is automatically de-identified by the website and aggregated at the state level. E-mail addresses are collected on the site, but solely for website management, technical assistance, and user access. See Appendix A for full copy.

Workshop Data Collection Form. Several process measures will be collected to assess the effectiveness of the training and support delivered. All measures will be collected via survey at the completion of each training component or tracked by review of programmatic records (i.e., action plan, meeting minutes). Quantitative data collected for this aim will be analyzed using descriptive statistics. Qualitative analysis of programmatic records will be conducted following procedures outlined. See Appendix B for full copy.

Dosage delivered is the number of units of an intervention delivered or provided.¹⁰¹ For this study, this measure will be defined by the number of hours of training and technical assistance provided to each state.

Dosage received is the extent to which participants engage with or use the materials provided.¹⁰¹ This will be measured by whether or not the action plan is completed and implemented, whether the workgroup utilizes the resources and materials provided, and the extent to which the action plan is implemented.

Participant reactions will be measured by the extent to which the participants felt that the objectives of the training and technical assistance were achieved, satisfaction with the training and technical assistance and perceived usefulness of the training provided.

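### Plan implementation in comparison states is promised as part of the dose analysis, but the dose measures are not specified on a scale common to both arms

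*Combined protocol and SAP*

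**What the plan says.** Section 5.1 (Comparison state protocol) allows that comparison states may adopt plans independently and states: "We will track implementation and account for it in analyses". Section 9.0, C.6.e, repeats the expectation, saying that "the level of adoption and implementation of action plans both from the training (intervention states) and from other initiatives (comparison states" will differ across programs and over time. It uses the Aim 1 dose and participant measures to calculate uptake of the training in intervention states and other actions in comparison states. Equation 1 contains one dose variable, D, and a group-by-dose product. D is not defined further.

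Section 10.0 gives two dose measures. For dose delivered, "this measure will be defined by the number of hours of training and technical assistance provided to each state". Dose received concerns the action plan: "This will be measured by whether or not the action plan is completed and implemented", together with the extent of implementation and use of the materials. On collection, "All measures will be collected via survey at the completion of each training component or tracked by review of programmatic records".

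Appendix B, part II, holds the dose-received items. Item 1 is "My program created a program sustainability action plan based on the results of the Program Sustainability Assessment Tool and Action Planning Training (Y/N". Item 3 begins "Please indicate the percentage of your sustainability plan your program has implemented", and items 4 and 5 ask for monthly staff time on the plan. Items 3 to 5 do not mention the training.

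For comparison states, section 5.1 lists the PSAT, record abstraction, and the manager interview and survey. It does not list the Appendix B form. Abstraction covers all 24 states at three time points, and section 10.0 names action-plan implementation as an example variable.

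**The concern.** Sections 1.0 (Innovation and Objectives) say that every state funded under the 2015 CDC announcement must write a sustainability plan and report on carrying it out. Independent planning in the comparison arm is therefore likely, and it is the main influence that could narrow the contrast between arms. To interpret a small or null difference, the analyst needs to know how much planning each arm did, measured the same way. If the dose variable reflects only what the study supplied, it carries no information on this. If one source is used for trained states and another for the rest, the difference in instrument coincides with arm. The choice of D also decides whether Equation 1 can be fitted as written.

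**Working it through.** The plan gives no figure for dose. Its one calculated figure, about 9 programs per group (effect size 1.25, power 0.8, alpha 0.05), reproduces as a one-sided two-sample t-test: n = 8.68, rounded up to 9, and 9 × 4/3 = 12. It does not depend on the dose measure and is not in question here.

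**1. What each source can record for a comparison state with its own plan**

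- *Hours delivered (section 10.0):* nothing about the plan. The state receives the shared webinar, a PSAT report with follow-up correspondence, and a resource packet. Study hours are 0, or 45/60 = 0.75 if the webinar counts.
- *Appendix B, item 1:* No, because the plan did not come from the study training.
- *Appendix B, items 3 to 5:* answerable as worded, if asked. The lowest answers are 10% or less (item 3) and under 1 hour a month (items 4 and 5). A state with no plan cannot be told apart from one whose plan has barely started.
- *Record abstraction:* implementation can be recorded, from public records only, but no rule turns it into D.
- *PSAT, Strategic Planning item 3:* asks both arms whether a sustainability plan exists. It is part of the PSAT score, which is itself an outcome, so using it as exposure would put part of the outcome on both sides of the model.

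**2. Equation 1 with D in hours**

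Let D = c in every comparison-state row.

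- Intervention rows (G = 1): G×D = D.
- Comparison rows (G = 0): G×D = 0 = D − c.
- Together: G×D = D − c + c×G.

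The product is an exact linear combination of the intercept, D and G:

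- c = 0: G×D = D.
- c = 0.75: G×D = D − 0.75 + 0.75×G.

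A numerical check used 24 states × 2 follow-up times = 48 rows and five columns (intercept, baseline PSAT, G, D, G×D). The rank was 4 of 5 for either value of c. Further covariates cannot remove the dependence. β3 and β4 are not separately estimable.

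If the product is dropped and c = 0, the coefficient of G compares a trained state at zero hours with a comparison state. That is not the effect of the training.

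**3. Equation 1 with D as share of own plan implemented**

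The dose values and the number of comparison states with plans were assumed, since the documents give neither. With none of the 12 comparison states having a plan, the rank is 4 of 5. With 1, 2, 3, 6 or 12 having one, and implementation varying, the rank is 5 of 5.

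**4. Equation 1 with D as the number of stakeholders completing the PSAT**

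The rank is 5 of 5, but this count says nothing about plan implementation.

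**The case against.** The strongest reply is that a common source already exists. Two trained evaluators abstract records in all 24 states with one standardised tool and inter-rater checks. Action-plan implementation is a named variable, and the CDC progress reports they read should describe plan execution. Items 3 to 5 could also be put to any state. The rank problem arises only if D is hours, which Equation 1 does not say. Even then only the interaction is lost, while a group term and a dose slope within the intervention arm can still be fitted. Some material may also lie elsewhere: C.6.e points to C.5.d and C.5.e, which do not appear under those labels in the available text, and the manager survey instrument is not reproduced.

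Most of this stands, and it limits the point. A reader might infer that comparison states score zero on dose by construction, that a common scale is impossible, or that the form would show 0 of 12 comparison states with plans when all 12 have one. The documents support none of these. Items 3 to 5 are source-neutral, abstraction covers both arms, and a state never given the form has missing data, not a zero. Nor does the plan say that self-report will be used in one arm and records in the other.

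The reply does not close the gap. C.6.e assigns the comparison-state accounting to the Aim 1 dose measures, not to abstraction, and nothing visible connects the abstracted variable to D. Abstraction is confined to public records, while the workshop measures can also draw on action plans and meeting minutes.

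**Conclusion.** The point holds as a gap in specification and data collection: the promised accounting is not set up on a common scale. With hours as D, constant at 0 or 0.75 in comparison states, Equation 1 has rank 4 of 5. With a plan-implementation measure it has rank 5 of 5, provided at least one comparison state has a plan and implementation varies. The result for hours assumes that logged hours do not vary among comparison states. If webinar or follow-up time did vary slightly, the interaction would be estimable in form but would rest on that small variation.

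It would be too strong to infer that the trial cannot answer its main question. The CDC requirement applies to both arms, so the randomised contrast still estimates what the training adds to it. What is at risk is the dose analysis and the explanation of a small or null difference. The number of comparison states that will have plans is not given and could be anything from 0 to 12.

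**What to change.** - Reword Appendix B item 1 to ask whether the program has a written sustainability action plan from any source. Ask separately whether it came from the study training.
- Add a no-plan answer to items 3 to 5.
- Put these items to program managers in all 24 states through the existing key informant survey, at baseline and in June of years 2 and 3. Section 5.1 limits that survey to metrics not found in reporting records, so add a one-sentence exception.
- Define D in Equation 1 as this measure in both arms, cross-checked against the abstracted records.
- Keep training and technical assistance hours as a process measure within the intervention arm, outside the group-by-dose term.
- Test Hypothesis 1 on the group effect without dose adjustment, and report dose models as secondary. Plan implementation follows randomisation and lies on the causal pathway, so adjusting for it could remove part of the effect under test.

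The cost is a few survey items and a small amendment to the instrument, with no new contacts. Asking comparison managers about plans may prompt some planning, though the CDC requirement already does so.
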